2 SYNOPSIS

Protocol Number:

V-122

Title:

A phase I, open-label study to evaluate the safety, tolerability, and immunogenicity of UB-612 vaccine in healthy adult volunteers

Investigational Product:

UB-612 vaccine

Phase:

Phase I

Objectives:Primary Objective:

To evaluate the safety and tolerability of the UB-612 vaccine in healthy adults.

Secondary Objective:

To evaluate the immunogenicity of the UB-612 vaccine in healthy adults.

Study Design:

This is a phase I, open-label, dose-escalation clinical study to evaluate the safety, tolerability and immunogenicity of 3 ascending doses of UB-612 COVID-19 vaccine in healthy adults. This study will be carried out in three groups:

- (1) A group: 2 doses of UB-612 vaccine 10 µg
- (2) B group: 2 doses of UB-612 vaccine 30 µg
- (3) C group: 2 doses of UB-612 vaccine 100 µg

The 20 subjects in A group will be enrolled to receive two doses of 10 µg UB-612 vaccine at 28-day interval (Day 0, Day 28). If there is no safety concern regarding the UB-612 vaccinations in A group as determined by data and safety monitoring board (DSMB), the subjects in B group will be enrolled. Then subjects in C group will be recruited if no safety concerns after DSMB reviewed safety data in B group. The interim analysis will be performed when the last subject of each group completed Visit 9 (Day 56).

In each group, the first 6 subjects will be enrolled as a sentinel group to receive 1st vaccine and return at Day 3 and Day 7. If the 6 subjects in sentinel group have no \geq grade 3 adverse reactions or serious adverse events (SAEs) related to vaccine till Day 7 as determined by DSMB, the remaining 14 subjects could be enrolled. After all subjects in A group completed Visit 4 (Day 7), DSMB will determine if B group recruitment could be initiated after review the safety data of A group. Recruitment of B and C group will follow the same schedule.

In this trial, there will be 11 clinical visits. Subjects will come to the clinics at Visit 1 (screening, Day -14 ~ -1), Visit 2 (Day 0, baseline, 1st vaccination), Visit 3 (Day 3, only for first 6 subjects in each group), Visit 4 (Day 7), Visit 5 (Day 14), Visit 6 (Day 28, 2nd vaccination), Visit 7 (Day 35), Visit 8 (Day 42), Visit 9 (Day 56), Visit 10 (Day 112, 3 months after 2nd vaccination), and Visit 11 (Day 196, 6 months after 2nd vaccination).

In all groups, an informed consent and the eligibility of subjects will be checked at screening period. The 1st study vaccine administration will be done immediately after blood draw at Visit 2 to evaluate baseline laboratory safety and humoral / cellular immune response. The first 6 subjects in each group will be closely monitored by the study staff at least 2-4 hours after vaccination, and subsequent 14 subjects in each group will be monitored at least 60 minutes after vaccination (for vital signs change and adverse events). The post-vaccination diary card for 7-day solicited adverse events after vaccination will be given to subjects with a suitable instruction. The first 6 subjects in each group will visit clinics at Visit 3 (Day 3) and Visit 4 (Day 7) for monitoring safety, and 14 subsequent subjects could be enrolled if no \geq grade 3 AE or SAE related to vaccine is reported.

At Visit 4 (Day 7), subjects will return for laboratory safety check and have blood drawn for cellular immune response and hand in the diary card.

At Visit 5 (Day 14), the subjects will return to clinics and have blood drawn for humoral immune response.

At Visit 6 (Day 28), the 2nd study vaccine administration will be done after blood draw for humoral / cellular immune response and subjects will be closely monitored for 60 minutes after vaccination. The post-vaccination diary card will be dispensed to subjects.

At Visit 7 (Day 35), subjects will return for laboratory safety check and have blood drawn for cellular immune response and hand in the diary card.

At Visit 8 (Day 42), the subjects will return to clinics and have blood drawn for humoral immune response.

At Visit 9 (Day 56), the subjects will return to clinics and have blood drawn for humoral immune response.

At Visit 10 (Day 112) and Visit 11 (Day 196), the blood draws will be performed to observe the persistence of immunogenicity.

All adverse events and serious adverse events will be monitored from Day 0 until Day 196.

Number of Subjects:

Up to 60 subjects (20 subjects per group) will be enrolled into this study.

Treatment:

The UB-612 vaccines, 20 µg/mL, 60 µg/mL and 200 µg/mL, containing Adju-Phos[®] and UBI-1 Oligo (CpG1) adjuvant will be administered by an intramuscular (IM) injection, 28 days apart (on Day 0 and 28). The following dose regimens, 10 µg (0.5 mL), 30 µg (0.5 mL) and 100 µg (0.5mL), will be tested.

Subjects will be enrolled with sequential allocation to the UB-612 doses. After first 20 subjects in A group received 2 doses of UB-612 vaccine 10 µg, the next 20 subjects in B group will receive 2 doses of UB-612 vaccine 30 µg, and the final 20 subjects in C group will receive 2 doses of UB-612 vaccine 100 µg. All 3 groups vaccinations will be 28 days apart. The subjects in next ascending cohort will be enrolled only granted by DSMB after reviewing safety data of preceding cohort who completed Visit 4 (Day 7).

Duration of Treatment: 6 months

Study Population:

To be eligible for study entry, subjects must satisfy all of the following inclusion criteria:

1. Healthy male or non-pregnant female between the age of 20 and 55 years at time of enrolment.
2. Women of childbearing potential and men must agree to practice medically effective contraception from first vaccination until 3 months after the last vaccination. The acceptable effective contraception methods include:
 - a. Male or female sterilization, implant, or intrauterine device;
 - b. Injectable, pill, patch, ring plus one barrier method*;
 - c. Two combined barrier methods*.

*Effective barrier methods are diaphragm, male or female condoms, sponge, or spermicides (creams or gels that contain a chemical to kill sperm).

3. Able to understand the content and possible risks of informed consent and willing to sign the Informed Consent Form (ICF).
4. Able to understand and agrees to comply with all study procedures and be available for all study visits.
5. Negative serological test for Hepatitis B surface antigen (HBsAg), HCV RNA and HIV antibody screening.
6. Negative in serum antibodies (IgG) against UBI SARS-CoV-2 ELISA.

-
7. Negative result of RT-PCR (Reverse Transcriptase PCR) screening of nasopharyngeal or throat swabs for SARS-CoV-2.
 8. Ear temperature $\leq 38.0^{\circ}\text{C}$.
 9. The body mass index (BMI) of 18-30 kg/m^2 , inclusive, at screening.
 10. Indexes of blood routine, biochemistry and other laboratory tests** are within the normal ranges, or not clinically significant as judged by investigators.

** The items of laboratory tests will include blood routine (CBC, including Hb, Hct, RBC count, WBC count, WBC differential and platelet count), biochemistry (ALT, AST, total bilirubin, creatinine), and HbA1c.
 11. Judged to be healthy by the investigator on the basis of medical history, physical examination, 12-lead ECG, vital signs (systolic/diastolic blood pressure, pulse rate, body temperature, respiratory rate), and clinical laboratory tests (blood biochemistry, routine) performed at screening.

Subjects will be excluded from the study if one or more of the following exclusion criteria is applicable:

1. History of anaphylaxis, urticarial, or other significant adverse reaction requiring medical intervention after receipt of a vaccine.
 2. Female who is pregnant or positive in pregnancy test at screening or just prior to each vaccination administration.
 3. Female who is breast-feeding or plans to breastfeed from the time of the first vaccination through 60 days after the last vaccination.
 4. Any acute illness, as determined by the study investigator 3 days before first vaccination.
 5. Evidence or history of clinically significant hematological, renal, endocrine, pulmonary, gastrointestinal, cardiovascular, hepatic, psychiatric, neurologic, or allergic disease (including drug allergies).
 6. Known history of SARS or MERS.
 7. Previous exposure to SARS-CoV-2 or receipt of an investigational vaccine product for the prevention of COVID-19, MERS or SARS.
 8. Subjects who take part in another clinical study within 12 weeks prior to the day of informed consent.
 9. With certain underlying medical conditions which are at increased risk for severe illness from COVID-19, such as chronic kidney disease, COPD (Chronic Obstruction Pulmonary Disease), serious heart conditions (e.g., heart failure, coronary heart disease, or cardiomyopathies), or with major chronic illness, such as asthma, diabetes, or thyroid disease, and other not well-controlled.
 10. Congenital or acquired angioedema.
 11. Immune deficiency/disorder, whether due to genetic defect, immunodeficiency disease or immunosuppressive therapy.
 12. Platelet disorder or other bleeding disorder may cause injection contraindication.
 13. Prior chronic administration (defined as ≥ 14 day of continuous use) of immunosuppressant or corticosteroids (equivalent to ≥ 20 mg daily of prednisone), cytotoxic treatment in last 6 months before first vaccination.
 14. Prior administration of immunoglobulins and/or any blood products in last 4 months before first vaccination.
 15. Prior administration of attenuated, nucleic acid (mRNA or DNA) or vectored vaccines in last 1 month before first vaccination or expectation of such vaccines in the month after the second vaccination.
 16. Prior administration of subunit vaccine or inactivated vaccine in last 14 days before first vaccination or expectation of receipt of such vaccines in the 14 days after the second vaccination.
 17. Current anti-tuberculosis(TB) therapy or history of TB.
-

-
18. Alcoholism or substance abuser.
 19. History of malignancy within 5 years prior to screening visit, except basal cell carcinoma of the skin and cervical carcinoma in situ.
 20. Any medical disease or condition that, in the opinion of the study investigator, may confound the results of the study or pose an additional risk to the subjects by their participation in the study.

Primary Endpoint(s):

- Occurrence of adverse reactions within 7 days after vaccination
- The percentage of subjects with \geq Grade 3 adverse events within 7 days after vaccination

Secondary Endpoint(s):

- Occurrence of adverse events (AE) till Day 56
- Occurrence of serious adverse events (SAE) till Day 56
- Occurrence of serious adverse events during the whole follow-up period (6 months)
- Occurrence of adverse events of special interest during the study period
- Changes of safety laboratory measures
- Geometric mean titer (GMT) of antigen-specific antibody (Anti-S1-RBD) on Day 14, 28, 42, 56, 112, and 196.
- Seroconversion rate (SCR) of antigen-specific antibody on Day 14, 28, 42, 56, 112, and 196.
- Geometric mean fold increase of antigen-specific antibody on Day 14, 28, 42, 56, 112, and 196.

Exploratory Endpoint(s):

- GMT of neutralizing antibody against SARS-CoV-2 on Day 14, 28, 42, 56, 112 and 196
- SCR of neutralizing antibody against SARS-CoV-2 on Day 14, 28, 42, 56, 112 and 196
- Geometric mean fold increase of neutralizing antibody against SARS-CoV-2 on Day 14, 28, 42, 56, 112 and 196
- Distribution of titers
- Correlation between the immune response detected by ELISA and live virus neutralization test
- Positive rate and level of antigen-specific interferon-gamma (IFN- γ) measured by ELISpot on Day 7, 28, 35, and 196
- CD4⁺ and CD8⁺ T cell responses using intracellular cytokine staining and flow cytometry on Day 7, 28, 35, and 196.

Sample Size Determination

No formal statistical sample size and power computations are performed since the objectives of the study are to assess the safety and immunogenicity of the study vaccine. In this study, twenty subjects will be involved in each vaccine dose group. A total of 60 subjects will be recruited.

Data and Safety Monitoring Board (DSMB)

To enhance the safety and integrity of the study data, a DSMB will evaluate clinical and laboratory safety data of the first 6 subjects (the Sentinel Groups) in each group to evaluate the risk of remaining 14 subjects, and a total of 20 subjects in each group before advancing to the next higher dose level/cohort. The DSMB will consist of an independent medical monitor, a statistician, and 1 or more experts in vaccinology who have experience serving on DSMBs. The DSMB members will review safety data and to provide a recommendation on dosage escalation, or early termination in case there is a concern regarding safety. Both the DSMB and the Sponsor must approve further immunization in case there is no concern of safety.

Statistical Analysis

The Safety Set (SS) will consist of all subjects receiving at least one injection of the UB-612 vaccine. The Safety Set is for safety evaluation in analysis.

The Full Analysis Set (FAS) will consist of subjects who receive two vaccinations, have at least one immunogenicity assessment after vaccination, and without SARS-CoV-2 infection between Day 0 and Day 56. Subject receive prohibited medication/treatment/vaccine during pre-specified period has impact on immunogenicity may exclude from the FAS set.

The modified intention-to-treat Set (mITT) will consist of subjects who receive at least one vaccination and have at least one immunogenicity assessment after the first or second vaccination. The mITT is also analysed for immunogenicity evaluation.

The Per Protocol Set (PPS) will be a subset of FAS. PPS includes subjects who receive two vaccinations, have at least one immunogenicity assessment on Day 42 or 56 after vaccination, and without SARS-CoV-2 infection between Day 0 and Day 56. Subjects who had major protocol deviations as determined by the Study Team or who received prohibited medication/treatment/vaccine during the pre-specified period **leading to an impact on immunogenicity will be excluded from the PPS set**. The PPS is also analysed for immunogenicity evaluation as a sensitivity analysis.

All safety assessments, including AEs, PEs, VS, and clinical laboratory evaluations, where indicated, will be presented using descriptive statistics for each vaccine group of UB-612. Data will be summarized for each vaccine group and overall.

All adverse reactions within 7 days after vaccination will be summarized with numbers and percentages by study vaccine group and each vaccination. The percentage of subjects with \geq Grade 3 adverse events within 7 days after vaccination will also be demonstrated by study vaccine group and each vaccination. AEs till Day 56 will be presented with number and percentage by system organ class, preferred term, and study vaccine groups. The number and percentage of SAEs till Day 56 will be displayed in summary table by study vaccine groups. The number and percentage of SAEs during the whole follow-up period (6 months) will be presented in summary table by study vaccine groups. Adverse events of special interest during the study period will be summarized with number and percentage from the mapping result by MedDRA.

Changes of safety laboratory measures will be summarized with descriptive statistics by study vaccine group and each time point. ANCOVA model with laboratory baseline values as covariate will analyze changes of safety laboratory measures for testing the difference among vaccine groups. Pair-wise comparisons of least square means from the ANCOVA model will be presented. Intra-group difference in safety laboratory measures will also be analyzed by paired t test.

If a subject is infected by SARS-CoV-2 between Day 0 and Day 56, immunogenicity data from he or she will not be included in analysis, but all SARS-CoV-2 infections occurred within 6 months after Day 56 should be documented and reported following the same procedure of SAE reporting, especial attention should be paid in case of the occurrence of vaccine-associated enhanced respiratory disease (VAERD).

Geometric mean titer (GMT) will be described by descriptive statistics and the 95% confidence interval for study vaccine group. Additionally, the difference among vaccine groups will be analyzed by ANCOVA model under log-transform data with baseline level as covariate, if appropriate. Pair-wise comparisons of least square means from the ANCOVA model will be presented. The reverse cumulative distribution plot will be provided to display the distribution of GMT by time points for each vaccine group.

Seroconversion rate (SCR) will be presented as count and percentage in frequency table, and the 95% exact (Clopper-Pearson) confidence interval will be provided as well. The group comparison among dose groups will be assessed by Fisher's exact test.

Geometric mean fold increase (GMI) in each study vaccine group is summarized by descriptive statistics and the 95% confidence interval for study vaccine group. The difference among vaccine groups will be analyzed by ANOVA. Pair-wise comparisons of least square means from the ANOVA model will be presented. The reverse cumulative distribution plot will be provided to display the distribution of GMI by time points for each vaccine group.

Safety Evaluations

Each subject must be carefully monitored for the development of any AEs throughout study period. Safety evaluations will be based on changes in physical examinations, vital signs and changes in laboratory parameters, and adverse event, including subject self-reporting.

All SARS-CoV-2 infections occurred within 6 months after the vaccination should be documented and reported following the same procedure of SAE reporting, and it is necessary to conduct a case investigation, Furthermore, the critically ill or dead cases need to continue to conduct special investigation, mainly to analyze where there is an ADE or VAERD phenomenon.

Schedule of Assessments

Scheduled visit	1	2	3	4	5	6	7	8	9	10	11/ET
Test & observations	Screening	1 st vaccination				2 nd vaccination				Month 3 follow-up ^g	Month 6 follow-up ^h
Day	-14~-1	0	3 ^c ±1day	7 ±1day	14 ±3days	28 ±3days	35 ±3days	42 ±3days	56 ±3days	112 ±5days	196 ±15days
Clinical assessment											
Informed consent	X										
Inclusion/Exclusion Criteria	X	X									
Contraindication for second vaccination						X					
Demographics	X										
Medical history	X	X									
Physical Exam ^a	X	X	X	X	X	X	X	X	X	X	X
Vital sign	X	X	X	X	X	X	X	X	X	X	X
ECG	X	X ⁱ				X ⁱ			X		
Laboratory assessment											
HBsAg, HCV RNA, HIV antibody tests	X										
Nucleic acid test (nasopharyngeal/throat swabs)	X										
Serum antibodies (IgG) against SARS-CoV-2	X										
Lab (Safety)											
Blood routine	X			X		X	X				
Biochemistry	X ^d			X		X	X				
Pregnancy(HCG/urine) ^b	X	X				X					X
Lab (Immunogenicity)											
Humoral immune		X			X	X		X	X	X	X

Scheduled visit	1	2	3	4	5	6	7	8	9	10	11/ET	
Test & observations	Screening	1 st vaccination					2 nd vaccination				Month 3 follow-up ^g	Month 6 follow-up ^h
Day	-14~-1	0	3 ^c ±1day	7 ±1day	14 ±3days	28 ±3days	35 ±3days	42 ±3days	56 ±3days	112 ±5days	196 ±15days	
response												
Cellular immune response		X		X		X	X				X	
Study Related Procedures												
Vaccination		X				X						
Dispense diary card ^e		X				X						
Return diary card ^e				X			X					
AEs/SAEs		X	X	X	X	X	X	X	X	X	X	
COVID-19 infection surveillance									X	X	X	
Concomitant Medication	X	X	X	X	X	X	X	X	X	X ^f	X ^f	

a: Body weight and height will be assessed at Visit 1 only.

b: Screening for pregnancy will be performed (serum β -HCG pregnancy test at screening and urine pregnancy test before vaccination on Day 0, 28 and 196, for WoCBP only). It is not required for postmenopausal or surgically sterilized women. A positive urine pregnancy test should be confirmed by a serum test. Serum pregnancy testing in lieu of urine pregnancy tests will not be considered a protocol deviation.

c: Only for first 6 subjects in each group.

d: HbA1c will be only assessed at Visit 1 only.

e: In case of e-diary, it is no dispensing or return activity.

f: Only record medication for SAE.

g: 3 months after 2nd vaccination

h: 6 months after 2nd vaccination

i: The ECG will be performed within 1 hour after vaccination.

ET: early termination

Blood collection at scheduled visits

Scheduled visit	1	2	3	4	5	6	7	8	9	10	11/ET
Test & observations	Screening	1 st vaccination				2 nd vaccination				Month 3 follow-up	Month 6 follow-up
Day	-14~-1	0	3±1	7±1	14±3	28±3	35±3	42±3	56±3	112±5	196±15
Blood volume (mL)											
HBsAg, HCV RNA, HIV antibody tests	2										
Serum antibodies (IgG) against SARS-CoV-2	2										
Lab (Safety)											
Blood routine	4.5			4.5		4.5	4.5				
Biochemistry	2.5			2.5		2.5	2.5				
Pregnancy (HCG/urine)	1										
Lab (Immunogenicity)											
Humoral immune response		5			5	5		5	5	5	5
Cellular immune response		35		35		35	35				35
Total blood collection	12	40	0	42	5	47	42	5	5	5	40

Total amount of blood collection: 243 mL.

* If HLA genotyping will be performed, additional 2 mL of blood sample will be collected.

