6.4 Secondary Endpoints

Safety:

- Occurrence of adverse events (AEs) till Day 56
- Occurrence of serious adverse events (SAEs) till Day 56
- Occurrence of SAEs during the whole follow-up period (6 months)
- Occurrence of AEs of special interest during the study period
- Changes of safety laboratory measures

Immunogenicity:

- Geometric mean titer (GMT) of antigen-specific antibody (Anti-S1-RBD) on Day 14, 28, 42, 56, 112, and 196.
- Seroconversion rate (SCR) of antigen-specific antibody on Day 14, 28, 42, 56, 112, and 196.
- Geometric mean fold increase of antigen-specific antibody on Day 14, 28, 42, 56, 112, and 196.

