7.4.5 Removal of Subjects

7.4.5.1 Removal of Subjects from Immunogenicity Analysis

Subjects may stop study vaccine and withdraw from the immunogenicity analysis for any of the following reasons:

- Subjects did not receive 2 doses of UB-612 vaccine (refer to Section 7.4.4).
- Administration of prohibited medication/treatment/vaccine during pre-specified period which was enough to interfere immunogenicity.

Subjects who do not comply with the protocol will be replaced. Subjects who stop study vaccine for any other reason (i.e., AE) will not be replaced.

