7.5.4.1 Prohibited Medication/Therapy

The following medications or treatments which may affect the immunogenicity and clinical efficacy assessments will be prohibited during study period:

- Immunosuppressant or corticosteroids, cytotoxic treatment
- Immunoglobulins and/or any blood products
- Investigational product (including drug, vaccine)
- Other registered vaccine could be administered after Day 56, and should be apart from nearest visit at least one month.

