10.2 Datasets or Populations Analysed

Safety Set

The Safety Set (SS) will consist of all subjects receiving at least one injection of the UB-612 vaccine. The Safety Set is for safety evaluation in analysis.

Full Analysis Set

The Full Analysis Set (FAS) will consist of subjects who receive two vaccinations, have at least one immunogenicity assessment after vaccination, and without SARS-CoV-2 infection between Day 0 and Day 56. Subject receive prohibited medication/treatment/vaccine during pre-specified period has impact on immunogenicity may exclude from the FAS set. The FAS set is the primary analysis set for immunogenicity evaluation.

Modified Intention-to-Treat Set

The modified intention-to-treat Set (mITT) will consist of subjects who receive at least one vaccination and have at least one immunogenicity assessment after the first or second vaccination. The mITT is also analysed for immunogenicity evaluation.

Per Protocol Set

The Per Protocol Set (PPS) will be a subset of FAS. PPS includes subjects who receive two vaccinations, have at least one immunogenicity assessment on Day 42 or 56 after vaccination, and without SARS-CoV-2 infection between Day 0 and Day 56. Subjects who had major protocol deviations as determined by the Study Team or who received prohibited medication/treatment/vaccine during the pre-specified period **leading to an impact on immunogenicity will be excluded from the PPS set**. The PPS is also analysed for immunogenicity evaluation as a sensitivity analysis.

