5.2 Background

In December 2019, a cluster of patients with pneumonia surfaced in Wuhan, China. The culprit was quickly identified as a beta-coronavirus that has never been reported before, and the disease was named by WHO as Corona Virus Disease 2019 (COVID-19) and the virus that causes it by the International Committee on Taxonomy of Viruses (ICTV) as SARS-CoV-2 [2, 3]. As of May 2021, a global outbreak has caused over 150 million confirmed cases in more than 220 countries or territories, with over 3 million deaths, making the SARS-CoV-2 pandemic a general public health event that has stirred up worldwide attention. Development of effective vaccines that prevent disease, viral shedding and transmission is urgently needed. At least 14 vaccines are now approved in one or more countries, but vaccine coverage is still in its infancy.

SARS-CoV-2 is a positive-strand RNA virus that belongs to the group of Betacoronaviruses. The genome of SARS-CoV-2 is approximately 29,700 nucleotides long and shares 79.5% sequence identity with SARS-CoV [4]. The long ORF1ab polyprotein at 5' end of the genome encodes 15 or 16 non-structural proteins, and the 3' end encodes 4 major structural proteins, including the spike (S) protein, nucleocapsid (N) protein, membrane (M) protein, and the envelope (E) protein [5]. SARS-CoV-2 interacts with the receptor angiotensin converting enzyme 2 (ACE2) on host cells via receptor binding domain (RBD) of its S protein for viral entry and subsequent

pathogenesis [6], resulting in severe respiratory illness with symptoms of fever, cough, and shortness of breath, and even death in severe cases [7].

Vaccines are the most effective and economical means to prevent and control infectious diseases [8]. The development and distribution of effective vaccines against SARS-CoV-2 infection are urgently required. Currently, multiple vaccines have demonstrated efficacy in randomized controlled trials, and global vaccinations campaigns are underway under Emergency Use Authorizations. However, Johns Hopkins University estimates on ~17% of the world population has received primary immunization against SARS-CoV-2. This shortfall in actual vaccinations underscores the need for additional vaccines [8].

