7.5.4.1 Prohibited Medication/Therapy

The following medications or treatments which may affect the immunogenicity and clinical efficacy assessments will be prohibited during study period:

- Investigational product (including drug, vaccine)
- Immunoglobulins and/or any blood products
- Immunosuppressant or corticosteroids, cytotoxic treatment
- COVID-19 vaccine other than study vaccine
- Other registered vaccine could be administered after Day 29 (subunit vaccine or inactivated vaccine could be after Day 15), and should be apart from Day 85 at least one month.

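### V-122 permits registered vaccines after Day 56 without excepting COVID-19 vaccines, and its immunogenicity sets remove only prohibited ones, so Day 196 titres could be another vaccine's response

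*Supplement*

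**What the plan says.** All references are to V-122 unless another protocol is named. V-123 and V-205 are separate studies, not later versions of V-122.

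- **Role of the FAS (10.2).** "The FAS set is the primary analysis set for immunogenicity evaluation".
- **Removal from the FAS (synopsis; same rule in 10.2).** "Subject receive prohibited medication/treatment/vaccine during pre-specified period has impact on immunogenicity may exclude from the FAS set". The trigger is a prohibited product, and removal is optional.
- **Removal from immunogenicity analysis (7.4.5.1).** The same trigger applies: "Administration of prohibited medication/treatment/vaccine during pre-specified period which was enough to interfere immunogenicity".
- **PPS and mITT (10.2).** The PPS drops subjects for major deviations or for prohibited products that affect immunogenicity. The mITT has no vaccine criterion.
- **What is prohibited (7.5.4.1).** Investigational products, vaccines included, are barred throughout the study. For the rest: "Other registered vaccine could be administered after Day 56, and should be apart from nearest visit at least one month". COVID-19 vaccines are not mentioned.
- **Late endpoints (6.4).** "Geometric mean titer (GMT) of antigen-specific antibody (Anti-S1-RBD) on Day 14, 28, 42, 56, 112, and 196", with seroconversion rate and fold increase on the same days. The synopsis and 7.1 give persistence as the purpose of the Day 112 and Day 196 samples.
- **Recording.** Section 7.5.4 has concomitant therapy recorded during the study period. Footnote f of the schedule restricts this at Visits 10 and 11 to medication for SAEs.

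For comparison, the V-123 list names as prohibited "COVID-19 vaccine other than study vaccine", and the V-205 list separately bars licensed COVID-19 vaccines for the whole study.

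**The concern.** A COVID-19 vaccine other than UB-612 can raise the antibodies that V-122 measures. A general rule on registered vaccines suits an influenza vaccine, where a month's spacing is meant to let non-specific effects pass. Spacing does not remove a specific antibody response to the same virus. If such a vaccine is permitted, receiving it is neither use of a prohibited product nor a deviation, so none of the removal rules applies.

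What is at stake is the interpretation of Day 196. Antibody raised by another product would be read as durable UB-612 immunity. If uptake differed between the 10, 30 and 100 µg groups, which were enrolled one after another, the comparison of dose groups at that visit would also be disturbed. Anti-S1-RBD is a secondary endpoint and neutralizing antibody an exploratory one. The primary endpoints are safety endpoints and are not affected.

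**Working it through.** V-122 gives no sample-size or power calculation, so there is no figure of its own to reproduce. Three questions can be checked.

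**1. Does the one-month rule close the gap?**

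Inputs: Visit 9 at Day 56 ± 3, Visit 10 at Day 112 ± 5, Visit 11 at Day 196 ± 15 (schedule, 7.2). The length of a month, m, is not defined, so I take 28, 30 and 31 days. A permitted day must lie after Day 56 and at least m days from both neighbouring visits:

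first permitted day = previous visit + m; last permitted day = next visit − m.

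| m | Before Day 112, nominal visits | Before Day 112, widest windows (Visit 9 on Day 53, Visit 10 on Day 117) | Before Day 196, nominal visits |
|---|---|---|---|
| 28 | Day 84 only | Day 81–89 | Day 140–168 |
| 30 | none (86 > 82) | Day 83–87 | Day 142–166 |
| 31 | none (87 > 81) | Day 84–86 | Day 143–165 |

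For m = 30 before Day 196: 112 + 30 = 142 and 196 − 30 = 166. That is 166 − 142 + 1 = 25 days, lying 30 to 54 days before the Day 196 sample. If Visits 10 and 11 fall at opposite ends of their windows, the range is Day 137–181 (107 + 30 to 211 − 30) at the widest and Day 147–151 (117 + 30 to 181 − 30) at the narrowest. It never closes.

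If the spacing were read as applying only to the next visit, Day 57–82 would be open before Day 112 at m = 30. Section 8.9 itself offers influenza vaccine at Visit 9, which does not fit a one-month distance from the nearest visit, so the text does not settle how strictly the rule is meant. On the strict reading, the exposure is essentially at Day 196.

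**2. Does any analysis set catch the subject?**

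Take a subject with both UB-612 doses, no infection to Day 56, and a registered COVID-19 vaccine on Day 150.

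- FAS and 7.4.5.1: the vaccine is not prohibited, so there is no removal.
- PPS: not prohibited and, being allowed, not a deviation on that account, so there is no removal.
- mITT: no vaccine criterion.
- Exclusion criterion 7: applies at entry only.

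The Day 196 titre therefore enters all three sets.

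**3. How far could a group summary move?**

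The documents give neither uptake nor a titre ratio. As assumptions, let k of 20 subjects have a Day 196 titre r times what it would otherwise be. A GMT is a mean on the log scale, so the group GMT is multiplied by r^(k/20).

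| k of 20 | r = 10 | r = 30 |
|---|---|---|
| 1 | 10^0.05 = 1.12 | 30^0.05 = 1.19 |
| 2 | 10^0.10 = 1.26 | 30^0.10 = 1.41 |
| 4 | 10^0.20 = 1.58 | 30^0.20 = 1.97 |

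For scale, V-123 Table 5-1 gives Day 56 anti-S1-RBD upper confidence limits relative to the GMT of 1029.839/526.98 = 1.95 (10 µg), 458.381/269.06 = 1.70 (30 µg) and 1082.350/805.11 = 1.34 (100 µg). Two such subjects would shift the 100 µg GMT by roughly its upper confidence margin, and the other two groups by less than theirs. For seroconversion, each subject lifted back over the four-fold threshold adds 1/20 = 5 percentage points.

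**The case against.** The case on the other side is substantial.

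- **Is a COVID-19 vaccine registered?** V-122 does not say whether an emergency-authorised product counts as registered or investigational. If investigational, it is already barred. This condition stands. V-123's exclusion 7 lists investigational and EUA products side by side, so it cannot be assumed that V-122's word investigational covers both.
- **Availability.** V-123's background states "At least 14 vaccines are now approved in one or more countries", but it is dated May 2021, calls coverage still very early and says nothing about access for these subjects. According to V-205 section 5.4, dosing began on 25 September 2020, which puts Day 142–166 for the first subject at about 14 February to 10 March 2021. Use of another vaccine is possible, not shown. This stands.
- **Vaccines outside the permitted days.** One given by Day 56, or within a month of a visit, breaches 7.5.4.1 and falls under the existing removal rules. This stands and narrows the point.
- **The SAP.** Section 10.1 leaves full analysis details to a SAP that is not shown, and omission of individual samples could be specified there. This stands in part. However, 10.2 already defines the sets, 7.5.4.1 expressly allows the exposure, and a SAP cannot act on a vaccination that was never recorded.

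Two stronger readings are tempting. A reader might infer that Day 112 is exposed as much as Day 196. The table shows it is not: with a 30- or 31-day month and nominal visits no permitted day precedes it. A reader might also infer that contaminated V-122 values would distort V-123, which compares its Day 85 with V-122 Day 112. That comparison is a paired test restricted to V-123 participants, and V-123's exclusion 7 bars prior recipients of investigational or EUA COVID-19 vaccines other than UB-612. Together with the narrow Day 112 exposure, this leaves no case worth making there.

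**Conclusion.** The point holds as a planning gap centred on Day 196. Followed as written, V-122 keeps a subject who received a registered COVID-19 vaccine on a permitted day (about Day 142 to 166) in every immunogenicity set and credits the resulting titre to UB-612. Day 112 is affected only with a 28-day month (Day 84 alone at nominal visits), at extreme visit windows, or under a looser reading of the spacing rule. Section 7.5.4 and footnote f conflict on what is recorded at Visits 10 and 11, so the exposure might not be detectable afterwards.

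The conclusion rests on a COVID-19 vaccine counting as registered and on at least one subject receiving one; the documents settle neither. The GMT multipliers are illustrations, not estimates, and no bias has been shown. That V-123 and V-205 both name COVID-19 vaccines separately indicates that the sponsor regards the distinction as material.

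**What to change.** 1. In 10.2 and the synopsis, for FAS, mITT and PPS alike, state that immunogenicity results obtained after receipt of any COVID-19 vaccine other than UB-612, whether registered, emergency-authorised or investigational, are omitted, while the same subject's earlier results are kept. Removing the whole subject, as the present rule may do, would discard valid early titres.
2. Ask for and record the date of any such vaccine at Visits 10 and 11. V-123 section 5.5 reports 59 of 60 subjects through Day 196 at a 13 May 2021 data cut, so for visits already past this means a retrospective query before database lock.
3. Reconcile 7.5.4.1, 7.5.4 and schedule footnote f with one another and with the analysis-set definitions. Say which category an emergency-authorised vaccine falls into, and how the one-month spacing fits the influenza vaccine offered at Visit 9. Which vaccines subjects may receive is a clinical decision for the sponsor; the analysis rule is needed either way.

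The cost is one analysis sentence, one dated CRF question at two existing visits, and wording changes. A few late titres may be lost, which slightly reduces precision at Day 196.
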